9.1 STATISTICAL HYPOTHESES

- Primary Outcome hypothesis:
 - Null: There is no difference in goal-directed behavior between baseline S-EEfRT and S-EEfRT during stimulation to dlPFC as a function of stimulation type (delta-beta TMS, theta-gamma TMS, or arrhythmic).
 - Alternate: There is a difference in goal-directed behavior between baseline S-EEfRT and S-EEfRT during stimulation to dlPFC as a function of stimulation type (delta-beta tACS, theta-gamma tACS, or active-sham).
- Secondary Outcome hypothesis:
 - Null: There is no difference in delta-beta phase-amplitude coupling strength between prefrontal electrodes and left motor electrodes for the decision period of the S-EEfRT as a function of stimulation type to dlPFC (delta-beta TMS, theta-gamma TMS, or arrhythmic TMS).
 - Alternate: There is a difference in delta-beta phase-amplitude coupling strength between prefrontal electrodes and left motor electrodes the decision period of the S-EEfRT as a function of stimulation type to dlPFC (delta-beta TMS, theta-gamma TMS, or arrhythmic TMS).
- Exploratory Outcome hypothesis 1:
 - Null: The impact of delta-beta TMS to dlPFC on goal-directed behavior is not correlated with personality traits related to motivation.
 - Alternative: The impact of delta-beta TMS to dlPFC on goal-directed behavior is correlated with personality traits related to motivation.
- Exploratory Outcome hypothesis 2:
 - Null: There is no difference in reward-evaluation between baseline S-EEfRT and S-EEfRT during stimulation to mPFC as a function of stimulation type (delta-beta TMS, theta-gamma TMS, or arrhythmic).
 - Alternate: There is a difference in reward-evaluation behavior between baseline S-EEfRT and S-EEfRT during stimulation to mPFC as a function of stimulation type (delta-beta tACS, theta-gamma tACS, or active-sham).
- Exploratory Outcome hypothesis 3:
 - Null: There is no difference in theta-gamma phase-amplitude coupling strength between prefrontal electrodes and posterior parietal electrodes for the decision period of the S-EEfRT as a function of stimulation type to mPFC (delta-beta TMS, theta-gamma TMS, or arrhythmic TMS).
 - Alternate: There is a difference in theta-gamma phase-amplitude coupling strength between prefrontal electrodes and posterior parietal electrodes the decision period of the S-EEfRT as a function of stimulation type to mPFCs (delta-beta TMS, theta-gamma TMS, or arrhythmic TMS).
- Exploratory Outcome hypothesis 4:

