9.2 SAMPLE SIZE DETERMINATION

The sample size is 24 participants in the final dataset to be used in analysis. However, to ensure that 24 participants complete the experiment, we conservatively estimate to enroll 50 participants as a ceiling for the sake of IRB approval. The motivation for the sample size of 24 participants in the analysis is explained below. The sample size is determined based on previous experiments from our group: the effect size of previous findings and the reliability of our estimates. Our estimators are precise due to sufficient number of trials per condition with each participant and that the tasks are titrated to the individual.

Primary outcome: Rhythmic TMS to lateral frontal cortex at delta-beta frequency will increase goal-directed behavior relative to arrhythmic TMS.

Previous Data: The planning and refinement of the proposed study was informed by our previous experiments that serve as preliminary data for the proposal. In our previous experiment, we delivered rhythmic TMS to lateral frontal cortex to increase performance in a cognitive control task (Riddle et al. 2020b). In our previous study, there was a significant interaction between TMS site and TMS frequency in a two-way repeated-measures ANOVA such that the improvement in performance in the cognitive control task was site and frequency-specific. The effect size from the partial-eta square was 0.23, and the effect from a dependent t-test was 0.532, with 20 participants. The experimental design of this previous study is similar to the current study in that there are two sites for stimulation (lateral frontal and medial frontal) with two different stimulation frequencies (delta-beta and theta-gamma). Both studies used an arrhythmic condition to control for non-specific effects of TMS.

Sample Size Determination and Power Calculation: Based on this previous effect size, we estimated that our participant count at 24 participants is powered at >95%.

[figure not shown]

Figure 3. Power calculation for the interaction effect in two-way repeated-measures ANOVA modeled as within factors interaction in a two-way ANOVA with partial-eta square of 0.23, and a correlation between variables of 0.77 based on Riddle, Scimeca et al. 2021. Power calculation run using the G*Power software. Proposed number of participants is 24 and is depicted in red.

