9.4 STATISTICAL ANALYSES

9.4.1 GENERAL APPROACH

All testing described below assumes a significance threshold of $p = 0.05$. Analyses will be deemed to be statistically significant if the p -value is less than this threshold. An analysis that does not exceed this threshold will be considered inconclusive. Continuous data will be described using means, standard deviations, and confidence intervals, while categorical data will be described using counts/percentages.

There may be additional covariates included in the analysis. Data will be assessed for normality and, if deemed necessary, corrective procedures will be applied (e.g., log normalization). Based on our previous dataset, we expect that the variables used here will be approximately Gaussian. However, if the distribution of a variable displays a skewed tail and a test for normality fails, then it is justified to use a corrective procedure. This correction will be applied upon consideration of the variables themselves, and not based on the result of the intended analysis.

Data will be collected until 24 participants complete the study and all data is usable. Given that recruitment will be feasible in a convenience sample, we expect to have complete data and all analyses will include the full participant pool. However, if there are technical errors that are not caught in time, then the affected analyses may have less participants. In this scenario, the data for a participant is then completely removed from the analysis.

The effects of stimulation are expected to be transitory, lasting for only a second or two after stimulation. For this reason, stimulation is delivered “online” immediately preceding the time at which the cognitive processes of interest are engaged. During each session, we include a control condition (arrhythmic TMS) that will be subtracted from the conditions of interest (delta-beta TMS and theta-gamma TMS). Therefore, we control for any effects of sequence or time within each session by subtracting each metric of interest from the condition-matched arrhythmic TMS metric. Furthermore, any learning effects from performing the reward-based decision-making task should be stabilized by the 3rd session. These methods are typical

in cognitive neuroscience paradigms. For the reasons listed above, it is unlikely that there will be any effect of sequence or carryover effects between sessions.

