9.4.2 ANALYSIS OF THE PRIMARY OUTCOME (BEHAVIOR)

Goal-directed behavior will be calculated as the average decision to perform the HARD task. The average of the two blocks for each stimulation conditions will be calculated (three stimulation types by two stimulation sites). A two-way repeated-measures analysis of variance (ANOVA) will be performed using within-participant factor of stimulation type (delta-beta TMS versus theta-gamma TMS; each subtracted by session-matched arrhythmic TMS) and within-participant factor stimulation site (dIPFC TMS versus mPFC TMS). We control for the effect of time with a subtraction of delta-beta TMS versus arrhythmic TMS and theta-gamma TMS versus arrhythmic TMS. In other words, four values are submitted to the ANOVA for each participant.

1. Delta-beta TMS to dIPFC minus arrhythmic TMS to dIPFC
2. Theta-gamma TMS to dIPFC minus arrhythmic TMS to dIPFC
3. Delta-beta TMS to mPFC minus arrhythmic TMS to mPFC
4. Theta-gamma TMS to mPFC minus arrhythmic TMS to mPFC

Thus, only differences from our active control, arrhythmic TMS, are considered meaningfully worth interpretation. We hypothesize to find an interaction between stimulation site and stimulation type in the ANOVA. Post-hoc differences will be investigated using Tukey's method to address multiple comparisons. We hypothesize that the predicted interaction will be driven by an increase in goal-directed behavior for delta-beta TMS to dIPFC. Sensitivity analyses will be conducted to evaluate the specificity of these effects: a similar analysis with reward-evaluation as the dependent variable and we do not expect that delta-beta TMS will have any effect on reward-evaluation.

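### The Tukey follow-up names no error term: a pooled one would misstate individual pairs, and the hypothesised effect against arrhythmic TMS is not a Tukey pair

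*Combined protocol and SAP*

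**What the plan says.** Section 9.4.2 averages two blocks for each of three patterns at each of two sites. It subtracts the arrhythmic mean of a session from the other two patterns in that session and runs a 2×2 repeated-measures ANOVA: "In other words, four values are submitted to the ANOVA for each participant". I call these values:

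- D1: delta-beta minus arrhythmic at dlPFC
- D2: theta-gamma minus arrhythmic at dlPFC
- D3: delta-beta minus arrhythmic at mPFC
- D4: theta-gamma minus arrhythmic at mPFC

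The predicted result is the site-by-type interaction, and its expected source is a rise under delta-beta TMS at dlPFC. The follow-up is one sentence: "Post-hoc differences will be investigated using Tukey's method to address multiple comparisons". Section 9.4.3 repeats all this for delta-beta coupling, and section 9.4.4 reuses the ANOVAs for exploratory outcomes 2 and 3.

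Section 9.4.2 also limits interpretation to differences from arrhythmic TMS. Section 9.2 states the primary hypothesis as a rise relative to arrhythmic TMS.

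The plan does not say which error term Tukey's method uses, which pairs form the family, or which comparison matters most. It does not mention sphericity.

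**The concern.** The interaction alone cannot show that delta-beta TMS at dlPFC is its source: a rise in D4 moves the interaction contrast in the same direction as a rise in D1. The attribution therefore rests on the follow-up tests, and two things are open there.

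First, the classical Tukey procedure applies one error variance to every pair. Here D1 and D2 contain the same arrhythmic mean, which cancels from their difference, whereas D1 and D3 contain two different arrhythmic means, which do not. A pooled error would then be too large for some pairs and too small for others.

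Second, the contrast that the hypothesis names is D1 against zero. The six Tukey pairs compare the four values with each other, so none of them tests it.

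**Working it through.** **The plan's own figure.** Section 9.2 gives power above 95%, for the interaction. Its inputs are "The effect size from the partial-eta square was 0.23, and the effect from a dependent t-test was 0.532, with 20 participants" and "a correlation between variables of 0.77".

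- f² = 0.23/0.77 = 0.2987.
- λ = f²·n·m/(1−ρ) with n = 24 and ρ = 0.77 is 62.3 for m = 2 and 124.7 for m = 4. Power exceeds 0.999, so the figure is reproduced in that form.
- Using partial eta squared or d = 0.532 directly, without the correlation term, gives 0.70 to 0.73. That is a separate matter.

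The plan gives no power for the follow-up tests.

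**Inputs.** From the documents: 24 participants, all within-participant; threshold 0.05; two-sided testing, because the alternative in section 9.1 is non-directional. Assumed, because the documents give no covariance: each condition mean has independent noise variance 1, and participants differ in their response to each pattern, consistently across sites, with variance t. I show t = 0 to 2.

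**Pair variances.**

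- Same site (D1−D2, D3−D4): the shared reference cancels, leaving 2 + 2t.
- Cross-site, same pattern (D1−D3, D2−D4): 4.
- Cross-site, different pattern (D1−D4, D2−D3): 4 + 2t.
- Pooled ANOVA error, applied to every pair: [2(2+2t) + 2(4) + 2(4+2t)]/6 = (20 + 8t)/6.

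The third variance exceeds the first by 2 whatever t is, so no t makes all six equal.

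**Error in the pooled standard error**, as √(pooled variance/pair variance):

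| t | pooled | same site | cross-site, same pattern | cross-site, different pattern |
|---|---|---|---|---|
| 0 | 3.33 | √(3.33/2): 29% too large | √(3.33/4): 9% too small | √(3.33/4): 9% too small |
| 0.5 | 4.00 | √(4/3): 15% too large | √(4/4): correct | √(4/5): 11% too small |
| 1 | 4.67 | √(4.67/4): 8% too large | √(4.67/4): 8% too large | √(4.67/6): 12% too small |
| 2 | 6.00 | √(6/6): correct | √(6/4): 22% too large | √(6/8): 13% too small |

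**Power for D1 versus D2**, simulated with 24 participants and a standardised paired difference of 0.6. Critical values of the studentized range are 3.72 (69 df, pooled) and 3.91 (23 df, pair's own error).

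| t | pooled Tukey | Tukey with pair's own error |
|---|---|---|
| 0 | about 34% | 57% |
| 0.5 | 46% | 58% |
| 1 | 54% | 58% |
| 2 | 63% | 58% |

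At t = 2 the same-site pair loses nothing, but D1 versus D3 falls from 80% with its own error to 65% with the pooled one.

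**Error rates under the null.** About 1.1% per pair is intended.

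- Pooled error, t = 0: 0.14 to 0.16% within a site, 1.7 to 2.0% across sites.
- Pooled error, t = 2: about 1.1% within a site, 0.2% for cross-site same-pattern pairs, and 2.5 to 2.7% for cross-site different-pattern pairs.
- Familywise, over t = 0 to 2: 0.054 to 0.059 with the pooled error, 0.048 to 0.055 with pair-specific errors. If the interaction mean square were used instead, it would be 0.161 at t = 0 and 0.374 at t = 2.

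**Interaction.** D1−D2−D3+D4 cancels both arrhythmic means and has its own 1-df error. Simulated type I error is 0.05.

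**The case against.** A reader might infer that the planned Tukey test is wrong by construction. The documents do not support that: no error term is named, and Tukey's method with pair-specific errors holds familywise error near 5%. Unequal pair variances follow from the subtraction in the model above; a wrong standard error follows only if one common error is used.

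A reader might also infer that the key follow-up comparison loses much of its power. The plan names no key pair. The large loss is confined to the same-site pair at small t; it shrinks to about 2 to 4 points at t = 1 and is gone at t = 2. For delta-beta at dlPFC versus mPFC the direction reverses: the pooled error is too small below t = 0.5 and too large above it. Exploratory objectives 1 and 4 presuppose individual differences in response to TMS, so t = 0 is not a neutral default.

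Nor should the gain from a remedy be overstated. At t = 0, a paired t-test at 0.025 reaches about 70%. Only the step from 34% to 57% comes from the error term; the rest comes from testing fewer pairs, which is a choice of family and not an error in the plan.

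Finally, this is a follow-up step in a pilot, and the predicted interaction is tested correctly. All of this stands and limits the point. It does not settle which error term will be used, and it does not supply the missing test against arrhythmic TMS.

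**Conclusion.** The follow-up is under-specified in a way that can affect which individual comparisons are declared. Under a pooled error, some pairs have wrong standard errors at every t examined, but which pairs, by how much and in which direction depend on a covariance outside the documents. The worst case for the same-site pair is t = 0: a standard error 29% too large and power of about 34% instead of 57%. At t = 2 the cost has moved to delta-beta at dlPFC versus mPFC, about 15 points, while different-pattern cross-site pairs reject too often.

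Pooled familywise error stays near 5%, the interaction test is unaffected, and pair-specific errors remove the problem.

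The second part needs no covariance assumption: delta-beta versus arrhythmic TMS at dlPFC, the effect said to drive the interaction, is not tested by any Tukey pair.

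The figures assume equal, independent noise in the six condition means and a pattern response that is consistent across sites.

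**What to change.** In 9.4.2 and 9.4.3, replace Tukey's method with paired t-tests on each participant's own difference (own standard error, 23 df), Holm-adjusted over three named contrasts:

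- (a) delta-beta versus arrhythmic at dlPFC (D1 against zero);
- (b) delta-beta versus theta-gamma at dlPFC (D1−D2);
- (c) delta-beta minus arrhythmic, dlPFC versus mPFC (D1−D3).

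For exploratory outcomes 2 and 3 in 9.4.4, where the hypothesis concerns theta-gamma TMS to mPFC, use the mirror contrasts: theta-gamma versus arrhythmic at mPFC, theta-gamma versus delta-beta at mPFC, and theta-gamma minus arrhythmic, mPFC versus dlPFC. The delta-beta contrasts should not be carried over.

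Each test uses its own standard error, so none relies on equal variances across pairs. The strictest Holm level is 0.05/3 = 0.0167, less strict than the roughly 0.011 per pair under Tukey with six pairs.

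The cost is wording only. The remaining pairs become descriptive, reported with unadjusted confidence intervals.

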9.4.3 ANALYSIS OF THE SECONDARY OUTCOME (ELECTROPHYSIOLOGY)

Delta-beta phase amplitude coupling will be calculated between the phase of delta oscillations (2-3 Hz) in prefrontal electrodes (FCz and surrounding electrodes) and the amplitude of beta oscillations (15- 25 Hz) in left motor electrodes (C3 and surrounding electrodes). The instantaneous phase and amplitude of these oscillations will be calculated by averaging the signal in these two regions of interest, band-filtering the signal to the specified range, and then performing the Hilbert transform on the signal. Phase-amplitude coupling (PAC) is then calculated by creating a hybrid signal using the amplitude of beta oscillations in left motor electrodes and the phase of delta oscillations in prefrontal electrodes:

$$PAC = \left| \frac{\sum_{t=1}^N M * e^{i\theta}}{N} \right|, M \text{ is magnitude of beta oscillations, } \theta \text{ is angle of delta oscillations, } N \text{ is number of time points}$$

The PAC value is normalized by creating a null distribution by randomly shifting the beta timeseries by at least 10% of the number of time points. Then, PAC is calculated between the delta-phase timeseries and each of these randomly shifted beta-amplitude timeseries. Finally, PAC_z is calculated as the z-transformed true PAC value relative to the null distribution.

The average during the decision epoch of each trial of the task during stimulation will be calculated. The average of the two blocks for each stimulation conditions will be calculated (three stimulation types by two stimulation sites). A two-way repeated-measures analysis of variance (ANOVA) will be performed using within-participant factor of stimulation type (delta-beta TMS versus theta-gamma TMS; each subtracted by session-matched arrhythmic TMS) and within-participant factor stimulation site (dIPFC TMS versus mPFC TMS). We control for the effect of time with a subtraction of delta-beta TMS versus arrhythmic TMS and theta-gamma TMS versus arrhythmic TMS. In other words, four values are submitted to the ANOVA for each participant.

1. Delta-beta TMS to dIPFC minus arrhythmic TMS to dIPFC
2. Theta-gamma TMS to dIPFC minus arrhythmic TMS to dIPFC
3. Delta-beta TMS to mPFC minus arrhythmic TMS to mPFC
4. Theta-gamma TMS to mPFC minus arrhythmic TMS to mPFC

Thus, only differences from our active control, arrhythmic TMS, are considered meaningfully worth interpretation. We hypothesize to find an interaction between stimulation site and stimulation type in the ANOVA. Post-hoc differences will be investigated using Tukey's method to address multiple comparisons. We hypothesize that the predicted interaction will be driven by an increase in delta-beta coupling for delta-beta TMS to dIPFC. Sensitivity analyses will be conducted to evaluate the specificity of these effects: a similar analysis with theta-gamma coupling as the dependent variable and we do not expect that delta-beta TMS will have any effect on theta-gamma coupling.

9.4.4 ANALYSIS OF THE EXPLORATORY OUTCOMES

First exploratory outcome: personality traits of motivation

In our previous study and found that goal-directed behavior positively correlated with traits of motivation. Thus, we hypothesize that personality traits of motivation will positively correlate with the degree to which delta-beta TMS will increase goal-directed behavior. The analysis will be run as a Pearson correlation between the impact of delta-beta TMS to dIPFC on goal-directed behavior and individual differences in traits of motivation. To control for the specificity of this effect, this correlation will be compared to arrhythmic TMS, personality traits of anxious rumination, and reward-evaluation.

Second exploratory outcome: reward-evaluation

As described in section 8.1.2, we will calculate reward-evaluation to quantify the specificity of TMS on specific behavioral metrics of reward-based decision-making. We will run an ANOVA as described in the description of our primary outcome, but with the dependent variable as reward-evaluation instead of goal-directed behavior. We hypothesize based on our previous study that theta-gamma TMS to mPFC will increase reward-evaluation.

Third exploratory outcome: theta-gamma coupling

Using the method for calculating phase-amplitude coupling in section 9.4.3, we will calculate the coupling between the phase of theta oscillations in prefrontal electrodes (Fz and surrounding) with the amplitude of gamma oscillations in posterior parietal electrodes (PO4 and surrounding). We will run an ANOVA as described in the description of our secondary outcome, but with the dependent variable as theta-gamma coupling instead of delta-

beta coupling. We hypothesize based on our previous study that theta-gamma TMS to mPFC will increase theta-gamma coupling.

Fourth exploratory outcome: functional connectivity in frontal-striatal circuitry

Using the task-driven functional magnetic resonance imaging data, we will calculate the strength of functional connectivity between the dorsal striatum and the lateral prefrontal cortex. We hypothesize that individual differences in this functional connectivity strength will be predictive of the change in goal-directed behavior with delta-beta TMS. The analysis will be run as a Pearson correlation between the impact of delta-beta TMS to dlPFC on goal-directed behavior and individual differences in functional connectivity between dorsal striatum and dlPFC. To control for the specificity of this effect, this correlation will be compared to arrhythmic TMS, reward-evaluation, and functional connectivity between mPFC and ventral striatum.

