stimulator output until a motor evoked potential (MEP) is generated: defined as a near-instantaneous increase muscle activity greater than 200 microvolts. Next, the intensity of single pulse TMS will be lowered until a MEP is generated on five out of ten pulses. This is defined as the motor threshold for the participant (Rossi et al. 2009). If the motor threshold cannot be determined via MEP, the experimenter will use visible twitches instead of MEP. Participants will receive 15 pulses of patterned TMS at 80% of their motor threshold during every trial. Patterned TMS takes three different forms (Figure 2). Delta-beta TMS delivers bursts of three pulses at 20 Hz (50 millisecond inter-pulse interval) with an inter-burst interval of 3 Hz (167 milliseconds). Theta-gamma TMS delivers bursts of three pulses at 50 Hz (20 millisecond inter-pulse interval) with an inter-burst interval of 5 Hz (200 milliseconds). As a control for the frequency-specificity of patterned TMS, arrhythmic TMS is delivered with a randomized inter-pulse intervals that are generated for each trial. The duration of arrhythmic TMS is randomly selected from a uniform distribution between the duration of delta-beta and theta-gamma TMS. The minimum inter-pulse interval will be 20 milliseconds. Between every train will be at least 11 seconds. An inter-train-interval of 11 seconds or greater allows for any residual effects of stimulation to return to baseline. This intensity, inter-pulse-interval, and inter-train-interval is well within the safety guidelines set forth for repetitive TMS (Wassermann, 1998; Rossi et al., 2009) and has been used in similar paradigms as the one described here. For example, Hermiller et al. 2020 delivered two seconds of theta-gamma patterned TMS (30 pulses per trial) at 80% of motor threshold (Hermiller et al. 2020). In addition, many other studies have delivered trains of TMS at higher intensities, upwards of 120% of motor threshold, on every trial of a cognitive task (Thut et al. 2011; Hanslmayr et al. 2014; Albouy et al. 2017)(Riddle et al. 2019; Riddle et al. 2020c; Sauseng et al. 2009). During a TMS session, participants will complete six blocks of 30 trials each. The participant will receive stimulation in either delta-beta, theta-gamma, or arrhythmic in a blocked design (the same stimulation is delivered for every trial in a block). The sequence of blocks will be randomized and counterbalanced such that each participant received each condition of TMS for 60 trials total. The third and fourth session of the experiment will be both be TMS sessions, where TMS is delivered to either the dorsolateral prefrontal cortex (dlPFC) or to medial prefrontal cortex (mPFC). The order and TMS sites will be randomized and counterbalanced across participants. Thus, at completion of the full experiment, participants will have received 12 blocks of 30 trials each of stimulation (180 trials per TMS session). In addition, two abbreviated blocks of TMS to mPFC and dlPFC will be administered at the end of the first session to assess for tolerability of TMS.

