interest are controlled within session, upcoming blocks are not known to experimenter or participant, behavioral metrics are different patterns of decision-making within the same epoch of the task, all task sessions are meaningful to the outcomes of the study, and experimenter-participant interactions are kept to a minimum within the task.

Randomization

We will use computer code to randomize and counterbalance the sequence of blocks within each session. Each session includes six blocks of 30 trials each. Every trial within a block will be either delta-beta stimulation, theta-gamma stimulation, or arrhythmic patterned stimulation. The order of blocks will be randomized for each participant. We will enforce that the first three blocks and last three blocks include each stimulation condition and participants will not receive the same form of stimulation two blocks in a row. This randomization scheme ensures that each type of stimulation is delivered at various temporal phases across the overall session. Within each session, the incentive that is offered for each trial will be randomized and counterbalanced such that an equal number of low (\$2.50, \$3.00, \$3.50, \$4.00) and high (\$4.50, \$5.00, \$5.50, \$6.00) value incentives are offered. Finally, the sequence of receiving stimulation to dlPFC and mPFC over the 3rd and 4th session will be randomized and counterbalanced across participants. In addition, both of the stimulation sessions include conditions of active interest to the investigators and so there will be no systematic bias to devalue one of the sessions. These methods for randomization and counterbalancing will reduce the chances that some unforeseen pattern of TMS or task parameters will systematically bias behavior. Thus, the experimental design has been selected to rigorously support scientific integrity.

Preregistration

The hypotheses of this study that are explicitly described in this protocol will be pre-registered on ClinicalTrials.gov. This ensures that the write-up of all manuscripts that result from this project will be clear to define what was a hypothesized outcome and what findings are unexpected. Furthermore, this process prevents any exploratory findings to be framed as hypothesized findings. By clearly defining these planned analyses, bias is minimized in the analysis of these data.

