8.1.2 TASK PERFORMANCE

1. Goal-directed behavior: In the Streamlined Expenditure of Effort for Reward Task (S-EEfRT), goal-directed behavior is quantified as the percentage of trials in which the participant chose the HARD task instead of the EASY task. In our previous experiment, goal-directed behavior positively and significantly correlated with delta-beta coupling. Goal-directed behavior ranges from 0 to 100% and task difficulty is titrated to push goal-directed behavior down to <85%. In our previous use of this task, minimum goal-directed behavior was 23%. To ensure that task performance is properly titrated during the baseline session, we will increase the difficulty of both tasks (EASY and HARD) when the HARD task is chosen greater than 85% of the time, and decrease the difficulty of tasks when the HARD task is chosen less than 15% of the time. At the end of the baseline session, if that participant has selected to perform the HARD task greater than 85% of the time or less than 15% of the time, then this will be considered a screening failure and their participation will be discontinued.
2. Reward-evaluation: In the EEfRT, reward-evaluation is quantified as the slope of the linear fit of percentage HARD trials for each incentive level (\$2.50 to \$6 in \$0.50 increments), dependent variable, to the incentive level, independent variable. In our previous experiment, reward-evaluation positively and significantly correlated with theta-gamma coupling. In our previous experiment, the average reward evaluation was 15% per \$1. Participants are informed at the

beginning of task performance that the S-EEfRT is a game and that no additional monetary compensation will be provided.

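### The plan does not say how the reward-evaluation slope is fitted or weighted, and one permitted reading would lose up to about 20–23% of the choice information at no gain

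*Combined protocol and SAP*

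**What the plan says.** Section 8.1.2 defines the metric: "reward-evaluation is quantified as the slope of the linear fit of percentage HARD trials for each incentive level", with levels from 2.50 to 6.00 dollars in steps of 0.50, which makes eight levels. It gives no weighting rule, no unit of fit, and no rule for a level that was never offered.

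Section 9.4.2 describes the primary analysis of percent HARD: "The average of the two blocks for each stimulation conditions will be calculated (three stimulation types by two stimulation sites"). It also calls for a similar analysis of reward-evaluation as a check on specificity. Section 9.4.4, second outcome, refers to 8.1.2 for the metric and to the primary outcome for the model: "We will run an ANOVA as described in the description of our primary outcome, but with the dependent variable as reward-evaluation".

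On trial counts, section 4.3 states: "During a TMS session, participants will complete six blocks of 30 trials each", and "each participant received each condition of TMS for 60 trials total". On incentives, section 6.3 states: "Within each session, the incentive that is offered for each trial will be randomized and counterbalanced such that an equal number of low" and high values are offered. It promises no balance by individual level, block or stimulation condition.

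**The concern.** For percent HARD, the mean of two blocks of equal size is the same number as the pooled percentage, so it does not matter how blocks are combined. A slope through level percentages does not have this property. With few trials per level, the result depends on whether the fit is done per block or on the whole condition, and on whether a level seen once counts as much as a level seen seven times.

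The plan carries the block-averaging step over to a metric where it matters and settles neither choice. Two analysts could obtain different reward-evaluation values from the same trials, and some of the permitted choices are noisier than they need to be. The slope is used twice: in exploratory outcome 2 and in the specificity check of 9.4.2.

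**Working it through.** **Inputs.** Six blocks of 30 trials per session and three stimulation types (4.3); eight incentive levels and an earlier average slope of 15 percentage points per dollar (8.1.2); low/high balance over the session (6.3). Assumed, because the documents do not give them: mean HARD of 50% (65% gave the same losses), a linear choice curve, and independent binomial choices.

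**1. The plan's own count.** 6 blocks / 3 types = 2 blocks; 2 × 30 = 60 trials per condition per session. This matches 4.3.

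**2. Trials per level.** Per block 30/8 = 3.75; per condition 60/8 = 7.5; per session 180/8 = 22.5. The last is not a whole number, so the eight levels cannot be exactly equal even over a session.

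**3. Chance that a block lacks at least one level.**
- Independent draws: 8(7/8)^30 − 28(6/8)^30 + … = 0.1457 − 0.0050 + … = 14.1%.
- 15 low and 15 high in each block: each half has 4(3/4)^15 − 6(1/2)^15 + … = 0.0533, so 1 − (1 − 0.0533)² = 10.4%.
- Low/high balance over the session only: about 13% (simulated).

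**4. Benchmark for a trial-level fit.** The deviations of the levels from their mean are ±0.25, ±0.75, ±1.25 and ±1.75, with squares summing to 10.5. With 7.5 trials per level, Sxx = 78.75. At a flat 50%, SD = 0.5/√78.75 = 5.6 points per dollar, in line with the simulated 5.64–5.72.

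**5. Comparison of estimators.** 4,000 simulated sessions per scheme, 15 points per dollar, mean HARD 50%. SDs are in points per dollar. Loss = 1 − Var(trial-level fit on 60 trials) / Var(estimator), from unrounded values.

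| Incentive allocation | Blocks lacking a level | SD: per block, unweighted | SD: pooled, unweighted | SD: pooled, trial-level | Loss: per block | Loss: pooled |
|---|---|---|---|---|---|---|
| Low/high equal over session | 13.1% | 5.75 | 5.39 | 5.09 | 21.8% | 10.7% |
| 15 low, 15 high per block | 10.0% | 5.67 | 5.35 | 5.07 | 20.2% | 10.1% |
| Levels equal over session as far as possible | 9.9% | 5.67 | 5.27 | 5.07 | 19.9% | 7.3% |
| Levels balanced within condition | 3.0% | 5.45 | 5.03 | 5.02 | 15.1% | 0.3% |
| Levels balanced within block | 0% | 5.05 | 5.03 | 5.02 | 1.4% | 0.6% |

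Repeat simulations of the session-balanced schemes (rows 1 and 3) gave variance ratios of 1.25–1.30 per block and 1.08–1.13 pooled. As losses: 1 − 1/1.25 = 20% to 1 − 1/1.30 = 23%, and 1 − 1/1.08 = 7% to 1 − 1/1.13 = 12%.

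**6. Source of the loss.** A per-block fit that weights levels by trial count loses only 2–4% in the schemes without level balance within blocks or conditions. Most of the loss therefore comes from giving sparse levels equal weight, not from splitting by block.

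**7. Carry-over to the ANOVA.** Subtracting arrhythmic and forming contrasts adds independent sampling variances, each inflated alike, so the ratio is unchanged when choice noise is the only source of variance. True between-participant variation dilutes it. If that variation equals the trial-level sampling variance, a ratio of 1.25 becomes (1 + 1.25)/2 = 1.125, a loss of 11%. At three times that variance it becomes (3 + 1.25)/4 = 1.06, a loss of 6%.

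**The case against.** The strongest reply is that the plan never prescribes the poor estimator. Section 9.4.4 sends the calculation of the metric to 8.1.2 and takes only the ANOVA from the primary outcome; 8.1.2 speaks of a fit without mentioning blocks or weights. The averaging sentence in 9.4.2 follows the definition of percent HARD and could equally mean combining the blocks at each incentive level before fitting one slope. Section 6.3 also does not rule out balancing levels within blocks, in which case almost nothing is lost.

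All of this stands. A reader might infer that the plan fits an equally weighted slope in each block and so loses a fixed fifth of its information. The documents do not support that. Both features are possible readings of a silent text, the figure sets the least efficient reading against the most efficient estimator, and a missing level affects about one block in ten to one in seven, not blocks in general.

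The reply does not remove the gap. The text still leaves the unit of fit, the weighting and the handling of an absent level to the analyst, and nothing in 6.3 guarantees the favourable allocation.

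**Conclusion.** The gap is real and minor. With the low/high balance that 6.3 promises, or with levels equal only over the session, an unweighted slope loses up to about 20–23% of the choice information if fitted per block and averaged, and about 7–12% if fitted once on the pooled 60 trials. The loss is about 1% with levels balanced within blocks. These figures cover choice noise only, and true differences between participants in their response reduce them.

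In simulation with a linear choice curve the unweighted and trial-level slopes were all unbiased, so the issue is precision. The primary percent-HARD result is unaffected.

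Two further inferences are tempting but unsupported:
- A reader might translate the loss into a drop in power. The documents state no power for this outcome. The effect size in 9.2 comes from a different cognitive task, and the drop would depend on an unknown between-participant variance.
- A reader might argue that extra noise helps the expected absence of a delta-beta effect on reward-evaluation. Section 9.4.1 already treats a non-significant result as inconclusive, so it could not count as evidence of specificity.

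**What to change.** In 9.4.4 (second outcome) and the reward-evaluation sensitivity analysis in 9.4.2, with 8.1.2 brought into line, state: for each participant, site and stimulation type, reward-evaluation is the slope from one linear regression of trial-level choice (HARD = 1, EASY = 0) on incentive, over all 60 trials of that condition. A fit to level percentages weighted by trial count gives the same slope and may be named as equivalent. Then subtract the session-matched arrhythmic slope and run the ANOVA as planned.

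This settles the unit of fit, the weighting and the handling of absent levels together. It was at least as precise as the unweighted slopes under every allocation simulated, though only trivially so when levels are balanced within blocks. The cost is wording only: same data, same ANOVA, no extra trials.
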